#### Feasibility Studies – Older Adult

At the 12-week time point, research staff will send participants the same questionnaires that were sent following the completion of informed consent procedures, via a link to REDCap online, in addition to the Injury questionnaire (Stathokostas) that is measured in the RCT. At the 12-week time point, they will be provided an accelerometer to wear for 7-days, which they will return by mail.

The 12-week follow-up visit will be identical to the baseline visit, other than the consent process – which will not be repeated. Research staff will send participants the following questionnaires via REDCap online: Physical Activity Enjoyment Scale, Depression, Anxiety, Loneliness, Sociodemographics, Basic Psychological Needs Satisfaction, and the Perceived Motor Competence Questionnaire for Children (PMC-C). These surveys should take approximately 30 minutes to complete.

During the visits, which will take place in the Department of Physical Medicine and Rehabilitation Lab in the the HCAR building, research staff will take the participant's blood pressure, height and weight, administer two (2) balance and physical function assessments, and complete a submaximal stress test, using the identical protocol as in the above baseline visit.

These visits are estimated to take 45 minutes. Research coordinator will provide payment for completing the 12-week visit following receipt of the accelerometer.

Research participants who are unable to attend an in-person visit due to extreme circumstances will still complete the surveys via REDCap online. These circumstances include, but are not limited to, travel burden, severe weather, disease outbreak, and any recommendations by Penn State University or Penn State Milton S. Hershey Medical Center to stop in-person visits.

#### **7.2.16 6 and 12 Month Follow-Up Visit.**

RCT

The 6 and 12 month follow-up visits will be identical to the baseline visit, other than the consent process, which will not be repeated, as well as the 7-day accelerometer wear trial, which may be completed in lieu of an in-person study visit, should research staff determine the participant is either unable or unwilling to attend an in-person visit. Research staff will send participants the following questionnaires via REDCap online: Physical Activity Enjoyment Scale, Depression, Anxiety, Loneliness, International Physical Activity Questionnaire, Lubben Social Network Scale, Sociodemographics, Exercise program preferences, Competitiveness, Tobacco Use, Exercise Self-Efficacy, The Preference for and Tolerance of the Intensity of Exercise Questionnaire (PRETIE-Q), The Affective Exercise Experiences (AFFEXX) and the Perceived Motor Competence Questionnaire for Children (PMC-C). These online surveys should take approximately 30 minutes to complete. Household members will not complete these visits and surveys.

During the visits, which will take place in the Department of Physical Medicine and Rehabilitation Lab in the the HCAR building, research staff will take the participant's blood pressure, height and weight and a maximal stress test will be completed, using the identical protocol as in the above baseline visit. These visits are estimated to take 45 minutes. Research coordinator will provide payment for completing the 6 month visit and for completing the 12 month visit following receipt of the accelerometer.

Research participants who are unable to attend an in-person visit due to extreme circumstances will still be requested to complete both the 7-day accelerometer wear trial as well as surveys via REDCap online. These circumstances include, but are not limited to, travel burden, severe weather, disease outbreak, and any recommendations by Penn State University or Penn State Milton S. Hershey Medical Center to stop in-person visits.

#### **7.2.17 2021 Cohort: COVID-19 Design Modifications**

As described within subsection 7.1 (COVID-19 Design Modifications), an unforeseen exercise intervention cancellation occurred between the dates of January 10, 2022 and February 21, 2022, following Penn State University mandates to pause all in-person human subjects research. In addition, a follow-up halt in the normal delivery of the exercise intervention sessions occurred between the dates of February 21, 2022 and April 4, 2022, in an effort to recondition subjects to the exercise interventions and mitigate the risk of injuries. Following the aforementioned 3-month period, subjects among the 2021 cohort were requested to continue his or her study participation, in an effort to achieve six (6) continuous, uninterrupted months of standard delivery exercise intervention. As result of the aforementioned effects of the COVID-19 pandemic, this 6-month period will be treated as an individual 6-month data collection period entity, with subjects completing the listed 9- and 12-month measurements (7.2 Study Procedures, RCT) at the 3- and 6-month post-resumption of the normal delivery of exercise intervention time points, respectively.

#### **7.2.18 Video Collection for Quality Control and for Recruitment Facilitation**

At regular intervals during the project, sessions will be video recorded. All participants will be asked to sign a standard Media Consent for Communications Media during the consent process, though they will not be required to sign to be part of the project. During sessions that will be recorded, subjects will be asked if they specifically do not want to be on camera during that session. If so, subjects will be moved to an area that will not be video recorded. Sessions will be video recorded, using a digital video camera that records to removable media. Recording will be done either by study staff or a professional videographer who will be accompanied by study staff. Media will be stored on the network. Videos to facilitate recruitment will first be shared with all participants who are shown on camera and scenes will be removed if participants are not comfortable with the footage shown being made public. Scenes from these videos will be added to the recruitment video, posted at [www.exercisestudy.org](http://www.exercisestudy.org). Videos will also be reviewed by project staff to measure adherence to the intervention.

### **7.3 Duration of Participation**

#### RCT

All participants will be in the study for 12 months.

#### Feasibility Studies: Adolescent, Major Depressive

All participants will be in the study for approximately 2 months, including a one-time focus group (adults currently being treated for major depressive disorder only) and then the 2 months of PlayFit participation, which will start approximately one month later.

#### Feasibility Studies: Older Adult

All participants will be in the study for approximately 3 months, including a one-time focus group and then the 3 months of PlayFit participation, which will start approximately one month later.

## **8.0 Subject Numbers and Statistical Plan**

### **8.1 Number of Subjects**

Focus Groups:

We will enroll 100 subjects

RCT:

We will enroll up to 470 subjects.

Feasibility Studies:

We will enroll up to 50 subjects in each of the three studies, or up to 150 total. We hypothesize that access to PlayFit will increase the minutes of moderate-vigorous PA from 10 minutes per day (SD=20) at baseline to 20 minutes per day (SD=30) after 3 months. As there is a dose-response relationship between MVPA and mortality, a doubling of MVPA should be expected to lead to a 60% reduction in mortality [41]. To achieve 80% power for these differences (with an alpha of <0.05), we will enroll up to 50 subjects at baseline, anticipating losses to follow-up of no more than 8 (16%) after 8 weeks, leaving up to 42 for analysis.

## 8.2 Sample size determination

We hypothesize that average weekly indoor sports facility attendance will be similar between PlayFit and Group Fitness (2.5 times per week) at 6 months, but at 12 months, attendance at PlayFit will be higher than at Group Fitness (2.5/week v. 1.5/week), which will lead to significant fitness differences. The power and sample size calculations are based on three pieces of background data: First, that supervised group fitness activities, among untrained adults, appear to increase V02max by at least 4 units over 12 months. Casla and colleagues, for example, recruited breast cancer patients for a twice weekly group fitness program and observed a mean V02max gain from an average of 26.5 to an average of 32.6 over 12 weeks [80]. Second, that PlayFit, which includes short sprints typical of sports, will increase V02max by at least 2.5 units more than Group Fitness, owing to greater attendance. Hammami and colleagues, in a meta-analysis of 28 studies, observed fitness gains of 7-14% for recreational soccer [81] and, in 2015, Milanović noted a 24% increase due to 3 times weekly soccer among untrained adults [82]. We have conservatively estimated a 10% increase in fitness among PlayFit participants. Oja and colleague conducted a meta-analysis of various sports interventions and observed a mean change in V02max of 4.11 (95% CI; 1.10-7.12) in the 5 studies of recreational soccer [83], similar in design to how the 5 PlayFit games are played. Third, without intensive contacts, long-term adherence to typical fitness programs is poor. Dellavigna and colleagues observed that, among 7,752 fitness center members followed for three years, the average member attended 4.3 times per month, far below recommendations for improving fitness [64].

## 8.3 Statistical methods

The analysis of the main outcome measure will be performed by intent-to-treat, in which changes between baseline and twelve (12) full months of exercise intervention participation will be compared by conditions. Student's t-test will be used, though adjustment may be needed for any variables not controlled through randomization. If it is determined that the groups, by chance, are significantly different on other covariates, then we will include those covariates in secondary analyses.

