## 1.0 Objectives

### 1.1 Study Objectives

This study is designed to test the comparative effectiveness of two different exercise programs (PlayFit and Group Fitness) to inform our understanding how to best integrate community-based physical activity programs into routine settings for sedentary adults.

Fewer than 1 in 10 U.S. adults get the recommended amount of aerobic physical activity, greatly increasing their chances of heart disease, stroke, and other chronic conditions. Although physical activity (PA) reduces risk and treats many common health conditions, physicians are actually reducing how frequently they talk to patients about physical activity, largely in part, because they do not think their patients will not follow through with their recommendations. The core problem of disseminating physical activity remains the fact that so few people adhere to the recommendations long enough to benefit.

Although many barriers to physical activity are well known (e.g., time, cost), we believe that a key, modifiable, and underappreciated barrier is that most adults simply do not enjoy physical activity enough to do it regularly. While studies agree that people who enjoy exercise more are more likely to become active, no study to our knowledge has tested whether a program designed specifically to increase enjoyment, would lead to greater gains in activity and fitness.

We have developed and piloted such a program from 2015-2017, called PlayFit. The PlayFit exercise program involves adults coming together three times each week to play a range of sports, all modified to 1) reduce effort, 2) reduce injuries, and 3) reduce competitiveness. We intend to conduct a definitive study of the PlayFit program in a randomized controlled trial, assessing fitness gains in PlayFit compared to group fitness conditions.

**Primary Objective:** AIM 1: Test the impact of PlayFit, compared to a traditional Group Fitness exercise model, on fitness (V02max) and activity (MVPA) after 12 months. We hypothesize that PlayFit will improve fitness and activity greater than Group Fitness, and, that this will be mediated by greater gains in enjoyment and session adherence.

**Secondary Objectives:** AIM 2. Test the impact of PlayFit and Group Fitness on rates of injury, body weight, blood pressure, loneliness, depression, and anxiety. We hypothesize that PlayFit participants will see greater gains in these physical and mental health-related outcomes and have a similar injury rate.

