As result of an unforeseen, COVID-19-related, prolonged exercise intervention cancellation (occurring between the dates of January 10, 2022 and February 21, 2022, following Penn State University mandates to pause all in-person human subjects research) and halt in the normal delivery of the exercise intervention sessions (occurring between the dates of February 21, 2022 and April 4, 2022, in an effort to recondition subjects to the exercise interventions and mitigate the risk of injuries), participants among the 2021 cohort may be requested to continue his or her study participation beyond the 12-month time point, to achieve six (6) continuous months of normal exercise intervention delivery between the months of February 2022 and August 2022. As result of the aforementioned effects of the COVID-19 pandemic, the study will treat this 6-month period as an individual 6-month study entity, completing the listed 9- and 12-month measurements (7.2 Study Procedures, RCT) with subjects at the 3- and 6-month post-resumption of the normal delivery of exercise intervention time points, respectively.

Participants among the 2019 cohort enrolled in the trial between the months of June and December 2019. Exercise intervention-related activities began in the month of September 2019 and continued through February 2020, prior to being halted as result of the onset of the COVID-19 pandemic. 6-month study visits occurred between the months of December 2020 and February 2020, prior to being halted as result of the onset of the COVID-19 pandemic. 12-month study visits did not occur among participants in the 2019 cohort, as result of the prolonged, COVID-19-related suspension of in-person human subjects research.

Participants among the 2021 cohort primarily enrolled in the trial between the months of June and October 2021. Exercise intervention-related activities began in the month of July 2021 (among subjects first to enroll in the study) and continued through December 2021, prior to being halted as result of the COVID-19 case count surge and subsequent College of Medicine (COM) mandate to pause all in-person human subjects research. The aforementioned in-person human subjects research pause rendered the 6-month study visits not feasible (due to COM mandates), disrupting data collection activities considerably. Following a 3-month halt in the normal delivery of the exercise intervention sessions between the dates of

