## RCT

Participants will complete their first visit with research staff at Penn State Hershey, in the Physical Medicine and Rehabilitation Lab in the HCAR building or in the Lime Spring Outpatient Center in Lancaster. These visits are estimated to take 45 minutes. After the baseline visit, research staff will send RCT participants the following questionnaires, via a link to REDCap online: Physical Activity Enjoyment Scale, Depression, Anxiety, Loneliness, International Physical Activity Questionnaire, Lubben Social Network Scale, Sociodemographics, Exercise program preferences, Competitiveness, Tobacco Use, Exercise Self-Efficacy, The Preference for and Tolerance of the Intensity of Exercise Questionnaire (PRETIE-Q), The Affective Exercise Experiences (AFFEXX) and the Perceived Motor Competence Questionnaire for Children (PMC-C). After the baseline visit, research staff will send participants among the Older Adult Feasibility Study the following questionnaires, via a link to REDCap online: Physical Activity Enjoyment Scale, Depression, Anxiety, Loneliness, Sociodemographics, Basic Psychological Needs Satisfaction, and the Perceived Motor Competence Questionnaire for Children (PMC-C). These surveys should take approximately 30 minutes to complete.

Research staff will obtain signature of the informed consent document prior to the in-person visit. Before initiating any research-related activities at the in-person visit, a research staff member will take the individual's blood pressure and heart rate to screen for eligibility and safety. If blood pressure is  $> 160$  systolic OR  $>100$  diastolic OR heart rate is  $> 120$  bpm, research staff will suggest the individual to see a PCP to control their blood pressure or heart rate, and if they would like to still participate in our study they can be tested again in the future. Their PCP will be sent a critical value letter including the blood pressure or heart rate values that were abnormal, and the individual will receive a critical value letter from research staff via mail. Research staff will take the participant's height and weight. Letters will also be provided for critical values on the depression and anxiety measure, as these may be clinically relevant and may warrant an evaluation.

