### **7.2.8 Randomization.**

Once eligible participants who sign the informed consent and completed the baseline questions, research staff at each site will randomize the participant into one of two groups (group fitness, PlayFit) in a one-to-one ratio based on the following stratification factors: age (over and under 35) and gender. The randomization will be performed through REDCap, but participant will not be informed of the group assignment until the accelerometer has been received and the baseline online surveys have been completed. At that point, a project staff member will contact the participant to review the randomization assignment (group fitness, PlayFit) and orient the participant to the program, by explaining how sessions tend to run, what to bring, reviewing possible locations, discussing frequently asked questions and answering any additional question the participant may have. Additionally, the participant will be given the option to install the TeamSnap phone application in order to receive exercise session confirmation and cancellation notifications.

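### Low-severity free improvement: section 8.3 could analyse VO2max and MVPA by ANCOVA with baseline value, age stratum and gender, and drop covariate selection by baseline significance tests

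*Combined protocol and SAP*

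**What the plan says.** Aim 1 in section 1.1 tests the effect of PlayFit "on fitness (V02max) and activity (MVPA) after 12 months", so both outcomes sit under the primary objective. Section 8.3 is the whole efficacy analysis plan for the RCT. By intent-to-treat, it compares change from baseline to 12 months between conditions: "Student's t-test will be used, though adjustment may be needed for any variables not controlled through randomization". The next sentence adds: "If it is determined that the groups, by chance, are significantly different on other covariates, then we will include those covariates in secondary analyses".

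Section 7.2.8 randomises one-to-one "based on the following stratification factors: age (over and under 35) and gender". Neither factor appears in a stated model. Baseline VO2max is measured at the baseline visit (section 7.2.6). Baseline MVPA comes from seven days of accelerometer wear (section 1.2), and section 7.2.8 withholds the assignment from the participant until the device is back.

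**The concern.** Two things could be better at almost no cost.

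- **Precision.** A change score uses baseline by subtraction, which imposes a slope of 1. ANCOVA estimates the slope instead and is usually more precise. Leaving the stratification factors out of the analysis makes the t-test slightly conservative if they predict change. Precision matters here because fewer people than enrolled can contribute: "12-month study visits did not occur among participants in the 2019 cohort".
- **Choice of covariates.** In a randomised trial a significant baseline difference is a chance event, as section 8.3 itself recognises. Adjustment helps when a covariate predicts the outcome. Selecting on imbalance answers a different question, and the content of the secondary models cannot be known until the baseline tests have been run.

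**Working it through.** **The plan's own figures.** There is none to reproduce for this point. Section 8.2 gives a difference of 2.5 VO2max units, but no SD, correlation, significance level, power or dropout for the RCT. Only relative precision can be checked.

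**Inputs.** Let s be the baseline SD, k the follow-up SD divided by the baseline SD, and rho the baseline-to-follow-up correlation. All rho values are assumptions. For k, equal SDs (1) and 1.25 are assumptions. The value 1.5 is 30/20, from the MVPA planning values in section 8.1, "from 10 minutes per day (SD=20) at baseline to 20 minutes per day (SD=30) after 3 months". Those belong to the feasibility studies (other populations, 3 months) and serve only as an illustration.

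**Formula.** The within-arm variance of change is s²(1 + k² − 2k·rho). The residual variance after regression on baseline is s²k²(1 − rho²). The first exceeds the second by s²(1 − k·rho)², so in large samples the change score loses nothing only when k·rho = 1. The ratio, ANCOVA to change score, is

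k²(1 − rho²) / (1 + k² − 2k·rho), which is (1 + rho)/2 when k = 1.

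For example, at k = 1.5 and rho = 0.8: 2.25 × 0.36 / (3.25 − 2.4) = 0.81/0.85 = 0.953. The square root is 0.976, so the interval is 2.4% narrower.

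| k | rho 0.5 | rho 0.7 | rho 0.8 | rho 0.9 |
|---|---|---|---|---|
| 1: variance ratio | 0.75 | 0.85 | 0.90 | 0.95 |
| 1: interval narrower by | 13% | 8% | 5% | 2.5% |
| 1.25: variance ratio | 0.893 | 0.981 | 1.000 | 0.950 |
| 1.25: interval narrower by | 5.5% | 1.0% | 0% | 2.5% |
| 1.5: variance ratio | 0.964 | 0.998 | 0.953 | 0.777 |
| 1.5: interval narrower by | 1.8% | 0.1% | 2.4% | 12% |

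**Cost in degrees of freedom.** Baseline value, age stratum and gender use 3. The number analysed at 12 months is not stated, so 100 and 200 are illustrative and 470 is the enrolment ceiling in section 8.1. Simulated ratios of mean interval width, ANCOVA with all three covariates to the t-test on change, strata not prognostic, k = 1 (4,000 runs each):

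| Analysed | rho 0.5 | rho 0.7 | rho 0.8 | rho 0.9 |
|---|---|---|---|---|
| 100 | 0.880 | 0.938 | 0.963 | 0.990 |
| 200 | 0.873 | 0.929 | 0.956 | 0.983 |
| 470 | 0.869 | 0.925 | 0.952 | 0.978 |

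At k = 1.5 the gain vanishes at rho = 1/1.5 = 0.67. There the ratio was 1.016 with 100 analysed and 1.008 with 200 (3,000 runs each).

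**Strata and type I error.** If the strata explain a share R² of the variance of change, the actual level of the unadjusted test is about 2(1 − Φ(1.96/√(1 − R²))). At assumed R² of 0.01, 0.05 and 0.10 this is 4.9%, 4.4% and 3.9%: conservative, not inflated.

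**Covariate selection.** No arithmetic is needed. Section 8.3 makes inclusion depend on a significant difference between arms, and nothing in it refers to prognostic value.

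**The case against.** The strongest reply is that nothing is broken. The t-test on change is unbiased under randomisation and does not inflate type I error. At rho of 0.8 to 0.9 with equal SDs the gain is only 2.5% to 5% of interval width, and with the one pair of MVPA SDs in the documents it is 0 to 2.4% at rho 0.5 to 0.8. All of this stands and is why the severity is low.

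A second reply is that section 8.3 does give a rule. Read together, its two sentences supply a trigger (a significant difference) and a place for the result (secondary analyses). Age and gender are controlled through randomisation, so leaving them out fits the plan's wording. This also stands. A reader might infer that the primary result hangs on the baseline tests, but on this reading it does not. The weakness is confined to the secondary analyses.

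Other stronger readings also go beyond the documents:

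- A reader might infer that baseline is ignored. It is not: it enters by subtraction.
- A reader might count the RCT questionnaires in section 7.2.6, which include "Depression, Anxiety, Loneliness, International Physical Activity Questionnaire, Lubben Social Network Scale, Sociodemographics, Exercise program preferences, Competitiveness, Tobacco Use", and compute the chance that at least one differs significantly. Section 8.3 lists no covariates to be tested and states no test level. Some of those items are Aim 2 outcomes. No such probability can be derived.
- A reader might expect ANCOVA to mend the loss of the 2019 cohort's 12-month visits. It cannot: a participant lacking either value is absent from both analyses.

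A last reply is that the trial is well advanced, since section 7.2.17 describes 2022 events as past, and a late change of primary method needs justification. That is fair, and the fix provides for it. Which assessment counts as 12 months for the 2021 cohort ("subjects completing the listed 9- and 12-month measurements (7.2 Study Procedures, RCT) at the 3- and 6-month post-resumption") is a separate question and arises equally under the t-test.

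**Conclusion.** The point holds as a free improvement of low severity. The planned test is sound, but a better one is available from data already collected. With equal SDs the interval would be about 13% to 2.5% narrower for rho from 0.5 to 0.9. With a larger follow-up SD the gain can be near zero, and the worst case simulated (100 analysed, SD ratio 1.5, rho 0.67) was 1.6% wider. These sizes rest on assumed correlations and SD ratios, so no single figure can be claimed for this trial. The criticism of choosing covariates by baseline tests does not depend on those assumptions. Nothing here ranks VO2max above MVPA: Aim 1 names both.

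**What to change.** In section 8.3, replace the t-test sentence with:

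> Each main outcome (12-month VO2max and 12-month MVPA) is analysed by ANCOVA on arm, its own baseline value, age stratum (over/under 35) and gender.

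The comparison of change is preserved: with baseline in the model, the arm effect is the same whether the dependent variable is the follow-up value or the change.

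Delete the rule that selects covariates by baseline significance tests. State instead that any further adjusted analysis uses a list of variables, named in the plan and fixed before outcomes are compared by arm.

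Date the change and give the reason. Section 10.1 has the DSMB reviewing VO2max and accelerometry, with findings presented to investigators and staff, and does not say whether by arm; the record should state this. If outcomes have already been compared by arm, report the planned t-test alongside the ANCOVA.

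The cost is plan wording, a dated justification and 3 degrees of freedom. No new data are needed, and the participants analysed stay the same.
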